8.3.1.3 OTHER SAFETY OUTCOMES

Other safety outcomes such as slit lamp examination, dilated fundus examination, and lens stability will be summarized descriptively at each visit based on the implanted-eye population for the HMIOL Cohort 1 and HMIOL Cohort 2. For the preoperative and 3-month post-primary-surgery visits, the descriptive statistics will also be provided for the HMIOL-eye cohort.

8.3.2 EFFECTIVENESS OUTCOMES

The effectiveness outcomes will be analyzed based on the Implanted-eye Population and PP Population. The BCDVA will also be summarized based on the Best-case population as suggested by ISO. [REDACTED]

8.3.2.1 BCDVA

The LogMAR will be derived for BCDVA. The descriptive statistics for continuous variables will be used to summarize LogMAR BCDVA at each visit based on the implanted-eye population for the three different lens cohorts (HMIOL Cohort 1, HMIOL Cohort 2, and Fellow-eye Cohort). The data at preoperative and 3-month post-primary-surgery will also be summarized for the HMIOL-eye cohort.

Additionally, the number and percentage of eyes reaching BCDVA 20/40 or better at each visit will be prepared for Cohort 1, Cohort 2, and the Fellow-eye Cohort. The one-sided upper 95% confidence limit of the proportion of HMIOL eyes with 20/40 or better will be calculated based on the binomial distribution and compared to a target of 0.925. If the confidence limit is > 0.925 , then the null hypothesis of $p \geq 0.925$ will not be rejected.

The analyses will be repeated based on the Per Protocol Population and the Best-case Population.

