
Sample Size
	
The sample size of this feasibility study is first calculated based on ISO 11979-7:2014 (E) to evaluate the proportion of HMIOL-implanted eyes with BCDVA of 0.3 logMAR of better for all HMIOL Cohort (post optic exchange for HMIOL Cohort 2). The statistical hypotheses for the effectiveness are $H_0: p \geq 0.925$ and $H_a: p < 0.925$, where p is the proportion of HMIOL-implanted eye with BCDVA of 0.3 logMAR. Based on the binomial distribution with a one-side significance level of 0.05 and a true p of 0.85, a sample size of 100 eyes will provide a statistical power of about 75%; while a sample size of 200 eyes will provide a statistical power of about 95%. Therefore, a sample size of 100 to 200 eyes implanted with HMIOL will be required for the study. For any adverse events that are not observed during the study, the one-sided upper 95% confidence limit of the adverse event rate is 0.0362 if the sample size is 100 eyes. The one-sided upper 95% confidence limit of the adverse event rate is 0.0183 if the sample size is 200 eyes. Therefore, a sample size of 100 to 200 deems to be sufficient for evaluating the safety and effectiveness of HMIOL for this feasibility study.
 
[REDACTED] [REDACTED] [REDACTED] [REDACTED]

	
[REDACTED]
 
The goal will be to enroll up to 200 subjects. However, after the first 25 subjects have reached the 3 month time point (and every 25 subjects thereafter), subject accountability and the rate of optic exchanges will be evaluated, and the enrollment goal will be reevaluated with respect to achieving the necessary sample size.
 
It should be noted that this is a feasibility study. All the analyses are to evaluate the effectiveness and safety of the HMIOL for the future confirmatory study. No adjustment is performed for the multiplicity.

--	--

[REDACTED]

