4.7.1 EARLY STUDY TERMINATION

ClarVista has the right to terminate this study at any time. Reasons for terminating the study may include, but are not limited to, the following:

- The incidence or severity of adverse events in this or any ongoing studies involving the same technology (if applicable), indicates a potential health hazard to subjects
- Subject enrollment is unsatisfactory
- Data recording is inaccurate or incomplete.
- A minimum of 105 subjects has been enrolled in the study *and* a minimum of 44 optic exchanges has taken place.

In the event of premature study termination, appropriate notification will be given to the Investigators, IRB / ECs, and regulatory bodies as applicable. In addition, ClarVista (or designee) will instruct all Investigators to discontinue dispensing study materials or treatments, will ensure all subjects complete appropriate follow-up, and will arrange study closeout visits at each site as appropriate.

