8.1 SAMPLE SIZE CALCULATION

The sample size of this feasibility study is first calculated based on ISO 11979-7:2014 (E) to evaluate the proportion of HMIOL-implanted eyes with BCDVA of 0.3 logMAR or better for All HMIOL Cohort (post optic exchange for HMIOL Cohort 2). The statistical hypotheses for the effectiveness are H0: $p \geq 0.925$ and Ha: $p < 0.925$, where p is the proportion of HMIOL-implanted eye with BCDVA of 0.3 logMAR. The sample size based on the binomial distribution with a one-side significance level of 0.05 and a power at a true p of 0.85. The table below summarizes the sample sizes and the corresponding statistical power. For this feasibility study, a sample size of at least 100 subjects will provide a statistical power of at least 75% to accept the alternative hypothesis of $p < 0.925$ if the true p is 0.85.

Sample Size	Statistical Power
100	0.753
110	0.785
120	0.813
130	0.837
140	0.858
150	0.876
160	0.891
170	0.905

It should be noted that this is a feasibility study. All the analyses are to evaluate the effectiveness and safety of the HMIOL for the future confirmatory study. No adjustment is performed for the multiplicity.

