8.3 STATISTICAL METHODS

The data analyses will be based on the analysis populations described above. No imputation for missing data will be performed. The statistical summaries will be prepared for HMIOL Cohort 1, HMIOL Cohort 2, and HMIOL eye Cohort (Cohort 1 + Cohort 2). For some selected outcomes, the summaries will be prepared for the fellow eye cohort.

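### The BCDVA comparison with 0.925 can detect a shortfall but cannot show that the target, or any floor, is met, and no lower limit for this proportion is planned in the visible text

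*Protocol*

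**What the plan says.** Protocol 8.1 sets H0: p ≥ 0.925 against Ha: p < 0.925 for the All HMIOL Cohort, where p is the proportion of eyes with BCDVA of 0.3 logMAR or better. Cohort 2 eyes are counted after their exchange. The calculation uses a "one-side significance level of 0.05 and a power at a true p of 0.85", and concludes that at least 100 subjects "will provide a statistical power of at least 75% to accept the alternative hypothesis of" p < 0.925. The table gives power from 0.753 at 100 eyes to 0.905 at 170. The synopsis adds about 95% at 200 eyes and concludes that "a sample size of 100 to 200 deems to be sufficient for evaluating the safety and effectiveness of HMIOL" in this feasibility study.

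Protocol 8.3.2.1 gives the decision rule: "The one-sided upper 95% confidence limit of the proportion of HMIOL eyes with 20/40 or better will be calculated based on the binomial distribution". The benchmark for this limit is 0.925, and H0 is retained whenever the limit lies above that value. The analyses are then repeated in the Per Protocol and Best-case populations.

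Two other places bear on the size of the problem. Section 8.3: "The statistical summaries will be prepared for HMIOL Cohort 1, HMIOL Cohort 2, and HMIOL eye Cohort (Cohort 1 + Cohort 2"). Section 4.7.1 lets the sponsor stop once 105 subjects are enrolled and "a minimum of 44 optic exchanges has taken place".

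**The concern.** The null hypothesis is that the lens meets the target, so the only conclusion the test can support at the 5% level is that the lens does not. A non-rejected null is compatible with the target being met, but it is also compatible with true rates well below it. An upper limit above 0.925 says nothing about how low the true rate might be.

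The study is meant to inform a confirmatory trial. The plan does not say what a non-rejected null may be taken to mean, and it plans no figure for the lower end of the plausible range. A reader of the report would know that 0.925 was not excluded, but not whether 0.85 was.

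**Working it through.** **Inputs.** Target 0.925, one-sided α of 0.05 and alternative 0.85 (protocol 8.1, 8.3.2.1). Sizes 100 to 200 (synopsis, Sample Size). Stopping minimum of 105 subjects and 44 exchanges (4.7.1). The limit is taken as the exact (Clopper-Pearson) binomial limit, and every eye is taken as evaluable.

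**Formula.** For n eyes, let c be the largest count with P(X ≤ c | n, 0.925) ≤ 0.05. H0 is rejected if X ≤ c. Power is P(X ≤ c | n, 0.85), and the chance of not rejecting is 1 − power. This is the same rule as comparing the exact upper 95% limit with 0.925.

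**The plan's own figures.** At n = 100, c = 87, since P(X ≤ 87 | 0.925) = 0.036 and P(X ≤ 88 | 0.925) = 0.071. Power = P(X ≤ 87 | 0.85) = 0.753, as stated. The other seven entries (n = 110 to 170) also match to three decimals. At n = 200 the exact power is 0.9585, against about 95% in the synopsis.

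**Chance of not rejecting, all HMIOL eyes, true p = 0.85.**

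| n | Smallest count not rejected | Power | Chance of not rejecting |
|---|---|---|---|
| 100 | 88 (88.0%) | 75.3% | 24.7% |
| 105 | 92 (87.6%) | 72.4% | 27.6% |
| 150 | 133 (88.7%) | 87.6% | 12.4% |
| 200 | 179 (89.5%) | 95.9% | 4.1% |

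**The 75% statement.** Exact power does not rise steadily with n, because c moves in whole eyes. At n = 104, c = 91 and power is 80.0%. At n = 105, c is still 91 and power falls to 72.4%. At 106 it is 73.7% and at 107 it is 74.97%. Between 100 and 200 these are the only three sizes below 75%, and the first of them is the plan's own stopping minimum.

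**What a non-rejected result leaves open.** For 92/105 the exact one-sided 95% upper limit is 0.9252, just above 0.925, and the lower limit is 0.810. The data would exclude neither 0.925 nor 0.85.

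**Cohort 2 alone (a hypothetical reading).** At n = 44, c = 37, and the chance of not rejecting at 0.85 is 50.3%. The smallest count not rejected is 38/44 (86.4%), with a lower limit of 0.749.

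**A lower limit above 0.85 as a benchmark.** At n = 105 it needs 96/105. The chance of meeting it is 3.7% at a true rate of 0.85, 73.8% at 0.925 and 96.2% at 0.95. At n = 200 it needs 179/200, the same count that escapes rejection under the present rule.

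**The case against.** The strongest case on the other side is that most of this is disclosed and proportionate. The 24.7% at 100 eyes is 1 minus the stated power, and at the enrolment goal of 200 the miss rate is 4.1%. The sizing is attributed to ISO 11979-7, and SAP section 4 says the formal tests are not meant to give definitive conclusions for regulatory approval. All of that stands and limits the severity. It does not tell a reader what non-rejection may be said to show, and it does not supply the missing lower limit.

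Several stronger readings are tempting but not supported:

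- *That non-rejection counts as success.* The protocol does not say so for BCDVA. The SAP uses that definition only for the ISO adverse event rates (5.4).
- *That 0.85 is an unacceptable rate.* The documents use it only as the alternative for power.
- *That the verdict in Cohort 2 is a coin toss.* Section 8.1 writes the hypothesis for all HMIOL eyes, and 8.3.2.1 computes the limit for HMIOL eyes. Section 8.3 provides for summaries by cohort, and the SAP plans separate analyses by cohort, but neither states this rule for Cohort 2 alone. The 50.3% applies only if someone extends the rule.
- *That this is the only formal effectiveness test.* A McNemar test on UCDVA is planned in Cohort 2 (8.3.2.3).
- *That each lost eye makes non-rejection easier.* This is true as a broad trend but not eye by eye: 104 eyes give 20.0% and 105 give 27.6%.

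The SAP supersedes the protocol's analyses (SAP section 2), and its Sample Size section is listed in the contents but cannot be read here. A rule or interval for BCDVA could stand there, so the point is confined to the visible text.

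**Conclusion.** The concern holds in a limited form. The comparison in 8.3.2.1 is a valid test for a shortfall from 0.925. It is not evidence that 0.925 or any floor is met, and nothing visible in the plan reports how low the rate could be. In the pooled eyes, the chance of not rejecting at a true rate of 0.85 is 24.7% at 100 eyes. Over the planned range of 100 to 200 it is highest at 105 (27.6%) and lowest at 200 (4.1%). The power claim in 8.1 is slightly wrong at the stopping minimum: 72.4% instead of at least 75%.

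These figures assume exact binomial limits and complete data. Missing values are not imputed, so evaluable numbers may be smaller; with 95 evaluable eyes the chance of not rejecting would be 31.7%. The weight is moderate: this is a feasibility study, and the remedy concerns reporting and interpretation, not design.

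**What to change.** In protocol 8.3.2.1 and the matching part of the SAP:

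1. Keep the upper-limit comparison with 0.925 for the pooled HMIOL eyes.
2. Report the exact two-sided 90% interval for the proportion with BCDVA of 20/40 or better in the pooled eyes, Cohort 1, Cohort 2 and the Best-case population. Its lower end is the one-sided 95% lower limit.
3. State that non-rejection will be reported only as *no shortfall from 0.925 detected*, and not as evidence that 0.925 is met.
4. State that the pass/fail comparison is not applied in Cohort 2 or in Best-case alone.

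In protocol 8.1, give the power as about 72% at 105 eyes.

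A lower limit above 0.85 can be offered as a descriptive benchmark if the sponsor wants one. It should not be a required criterion, because at 105 eyes a lens exactly on target would miss it about 26% of the time (1 − 0.738).

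The cost is a few sentences and one extra column in the BCDVA table. No subjects, visits or procedures are added.

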8.3.2.2 MBCDVA

The descriptive statistics for continuous variables will be used to summarize LogMAR mBCDVA with and without glare at 3-month post-primary-surgery visit based on the implanted-eye population for the HMIOL-eye Cohort.

8.3.2.3 UCDVA

The LogMAR will be derived for UCDVA. The change in the LogMAR UCDVA from pre-optic exchange to post-optic exchange will be calculated for each of the HMIOL Cohort 2 eyes. The change will be summarized descriptively with the 95% confidence interval of the mean change at each post-optic exchange visit. The proportion of eyes with UCDVA of 20/20 or better, 20/25 or better, 20/32 or better, 20/40 or better, and

worse than 20/40 at each visit will be summarized for the HMIOL Cohort 2 at pre-exchange and every post-exchange visit. The difference in the proportions will be compared by McNemar test.

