Regulatory Status	Feasibility (Pre-IDE)
Investigational Device	ClarVista HARMONI™ Modular Intraocular Lens System, non-toric aspheric optic
Objectives	
 • To demonstrate the feasibility of HARMONI™ IOL (HMIOL) implantation and assembly in subjects undergoing cataract surgery. • To demonstrate the feasibility of the HMIOL optic component exchange procedure (performed 3 months following primary cataract extraction)
Number of Clinical Sites and Study Subjects	Up to 200 subjects will be treated in this study at up to 7 investigational sites. Enrollment will be monitored as outlined in Sample Size section and adjusted accordingly.
Study Duration	
All subjects will have up to 18 months study participation (Cohort dependent – see Study Design) from time of consent to study exit.
 
Total study duration will be approximately 24 months.

Study Design	
Prospective, multi-center clinical study.
 
All subjects will be seen for a Preoperative Visit to capture baseline measurements then undergo cataract surgery with primary eye (first implant) receiving a test lens (HMIOL). The investigator will determine if the test lens is to be implanted in OD or OS based on target refraction and the best interests of the subject.
 
Safety and Effectiveness testing of the HMIOL design allows the Investigator and Subject to decide if an optic exchange in the primary study eye is in the best interests of the subject based on refractive outcome and target. This determination will be made at the 3 month visit.
 
At the 3 Month Visit (post-primary cataract extraction), subjects with satisfactory (as determined by investigator and subject) outcomes in the study eye, or those opting not to pursue an optic exchange, will be entered into

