	
 • [REDACTED] • [REDACTED] • AE rates as compared to ISO 11979-7:2014 Annex B Safety and Performance Endpoint (SPE) tables • [REDACTED] • Secondary Surgical Intervention (SSI) 
HMIOL Cohort 1
 
 • [REDACTED] [REDACTED] [REDACTED] [REDACTED] • AE rates as compared to ISO 11979-7:2014 Annex B SPE tables • [REDACTED] • SSI 
HMIOL Cohort 2
 
 • [REDACTED] [REDACTED] [REDACTED] [REDACTED] [REDACTED] [REDACTED] [REDACTED] [REDACTED] [REDACTED] [REDACTED] [REDACTED] • AE rates as compared to ISO 11979-7:2014 Annex B SPE tables • [REDACTED] • SSI (planned Optic Exchange procedures excluded) 
Effectiveness Endpoints:
 
All HMIOL Eyes Cohort:
 
 • Percent of eyes with post-operative BCDVA 20/40 or better by study Visit • Percent of eyes that achieve MRSE of ± 0.50 D of target by study visit • Percent of eyes that achieve MRSE of ± 1.00 D of target by study visit • BCDVA by study visit • UCDVA by study visit • mBCDVA (with and without glare) by study visit 
HMIOL Cohort 1
 
 • Percent of eyes with post-operative BCDVA 20/40 or better by study visit • Percent of eyes that achieve MRSE of ± 0.50 D of target by study visit
--	---

	
3) Uncorrected Near Visual Acuity (UCNVA) 4) Best Corrected Distance Visual Acuity (BCDVA) 5) Best Corrected Near Visual Acuity (BCNVA) 6) Mesopic Best Corrected Distance Visual Acuity (mBCDVA) 7) Slit Lamp Exam (SLE) 8) [REDACTED] 9) Intraocular Pressure (IOP) 10) Dilated fundus exam (DFE)
 
Masking Visual Acuity and Refraction testing will be conducted by study staff masked as to the subject's post-operative target SE up to the completion of the 3 Month Visit (post-primary cataract extraction). All other testing will be conducted by unmasked staff due to the expected unmasking from timing and frequency of the evaluation or visualization of the test article. [REDACTED] [REDACTED]

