Sulcus placement of a "piggyback" IOL is a procedure that has not been evaluated for safety and effectiveness by the FDA so the use of approved IOLs for this purpose in the U.S. is off-label. Among the complications reported with this procedure are secondary pigment dispersion, iris/pupil irregularities, chronic iritis, hyphema, glaucoma, zonular disruption and/or posterior capsular rupture. Thus, it would be desirable to be able to correct or modify the optical result without the need to implant a "piggyback" IOL with its inherent serious risks.

CLARVISTA MEDICAL

PROTOCOL CP-00001 Rev.05

IOL Exchange/Manipulation in general, is technically challenging for the surgeon and poses an iatrogenic risk to intraocular structures including the lens capsule, iris, and endothelium of the cornea. Manipulation of the capsular bag to remove an IOL is the major risk in this setting and can damage the capsular bag including posterior capsular rupture and capsular bag dislocation. The capsular bag cannot be repaired once damaged. This risk increases over time as the capsular bag adheres to the IOL and haptics. Even when IOL exchange is not required, manipulation of traditional IOL's to rotate or center the optic introduces the risk of capsular or zonular damage which can cause further lens instability and lens malposition. Thus, it would be desirable to be able to correct RRE without the need to remove the entire IOL particularly after capsular contraction or fibrosis.

The modular IOL concept will serve as a valuable addition to the armamentarium of cataract surgeons. The goal of this technology is to improve refractive (spherical and toric) outcomes and avoid the significant risks of secondary procedures currently being performed as standard practice to address RRE in an indirect manner. It is anticipated that this modular lens will provide clinical utility in two basic areas, the first being the focus of this study.

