1. Post-operative correction of residual spherical refractive error – Based on existing performance of conventional cataract surgery, researchers have concluded that refractive outcomes in normal eyes should be within 0.5D for 45% and within 1D for 85% of cataract cases³. This theoretical performance goal still falls substantially short of the real-world outcomes seen with corneal refractive surgery and which cataract patients and surgeons increasingly demand. As a consequence, secondary procedures to optimize visual outcomes following cataract surgery can be as high as 16% in some practices, particularly for premium lens patients².

Another common approach associated with residual spherical refractive error is referred to as monovision (which can be achieved with contact lenses, corneal refractive surgery, or IOL selection), a monofocal IOL which targets distance vision is used in the dominant eye and the opposite, the non-dominant eye is targeted for near vision. This approach allows patients to see at both distance and near and is a popular choice for patients wishing to achieve spectacle independence.

While it is commonly used for this purpose, not all patients are able to adapt to monovision.^{7,8,9,10} They may have difficulty with acuity-based tasks and with tasks demanding depth perception. Monovision patients may also experience problems with headaches and troublesome visual symptoms such as glare and halos around point sources of light, particularly under low-light conditions. Typically, within three months of the surgery a patient's acceptance or lack of acceptance of monovision correction will be known. At that point, dissatisfied patients are offered glasses to overcome the refractive disparity between eyes. Of course, this is contrary to the patient's desire to be independent of glasses. Furthermore, spectacle correction is not ideal due to the significant imbalance between the required lens power for each eye creating visual discomfort and intolerance (i.e. asthenopia). Refractive surgery on the cornea (e.g., LASIK or PRK) to reverse the over correction of the non-dominant eye is also an option, but not all monovision patients have a suitable cornea (e.g., too thin) and such surgery introduces additional risk.

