5.6. Effectiveness Endpoints

All HMIOL Eyes Cohort

- Percent of eyes with post-operative BCDVA 20/40 or better by study visit
- Percent of eyes that achieve MRSE of ± 0.50 D of target by study visit
- Percent of eyes that achieve MRSE of ± 1.00 D of target by study visit
- BCDVA by study visit
- UCDVA by study visit
- mBCDVA (with and without glare) by study visit

Cohort 1

- Percent of eyes with post-operative BCDVA 20/40 or better by study visit
- Percent of eyes that achieve MRSE of ± 0.50 D of target by study visit
- Percent of eyes that achieve MRSE of ± 1.00 D of target by study visit
- BCDVA by study visit
- UCDVA by study visit

Cohort 2 (Optic Exchange)

- Percent of eyes with post-operative BCDVA 20/40 or better by study visit
- Percent of eyes that achieve UCDVA by post-optic exchange study visit
 - 20/20 or better
 - 20/25 or better
 - 20/32 or better
 - 20/40 or better
 - Worse than 20/40
- Percent of eyes that achieve MRSE of ± 0.50 D of optic exchange target by post-optic exchange study visit
- Percent of eyes that achieve MRSE of ± 1.00 D of optic exchange target by post-optic exchange study visit
- BCDVA by study visit
- UCDVA by study visit

Fellow Eye Cohort

- Percent of eyes with post-operative BCDVA 20/40 or better by study visit
- BCDVA by study visit
- UCDVA by study visit
- Manifest refraction

Protocol CP-00001

ClarVista Medical, Inc.

Implanted-Eye Population: Eyes with successful HMIOL implantation. The effectiveness endpoints and exploratory measures will be summarized based on the implanted-eye population.

Per Protocol Population: Defined as study eyes with successful HMIOL implantation without a major protocol deviation (such as improperly enrolled in the study or lens power calculation errors). The protocol deviations will be reviewed and categorized by ClarVista clinical personnel prior to analysis. The effectiveness endpoints and exploratory measures will be assessed for the Per Protocol population and will be considered the primary population for effectiveness outcomes.

Best-Case Population: The Best-Case population is the PP population with all of the following characteristics:

- No clinically significant preoperative ocular pathology in the study eye, including any of the following present at the preoperative visit:
 - Pseudoexfoliation
 - Glaucoma
 - Uveitis
 - Retinal detachment
 - Diabetic retinopathy
 - Macular degeneration
 - Amblyopia

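### Cohort 2 UCDVA results pool all exchanged eyes whatever their target, so a deliberate change between near and distance targets would count as a gain or loss

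*Protocol*

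**What the plan says.** **UCDVA analysis.** Protocol 8.3.2.3 sets out three analyses, none with a condition on target refraction:

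- a change score: "The change in the LogMAR UCDVA from pre-optic exchange to post-optic exchange will be calculated for each of the HMIOL Cohort 2 eyes"
- its summary: "The change will be summarized descriptively with the 95% confidence interval of the mean change at each post-optic exchange visit"
- the proportions at 20/20, 20/25, 20/32 and 20/40 or better, and worse than 20/40, which "will be summarized for the HMIOL Cohort 2 at pre-exchange and every post-exchange visit", with the difference compared by McNemar test.

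SAP 5.6 lists the same categories ("Percent of eyes that achieve UCDVA by post-optic exchange study visit") and UCDVA by visit. SAP 4 sets the baseline at the 3 Month pre-exchange visit. SAP 9 splits UCDVA by cohort only. The McNemar test is not in the visible SAP.

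**Target refraction.** Protocol 3.2.1 limits lens power in the study eye to 18 to 26 D but sets no limit on target refraction, and the exchange exclusions in 3.2.4 do not mention target. The Synopsis (Study Design) states: "The investigator will determine if the test lens is to be implanted in OD or OS based on target refraction". It names the subject's interests as the other consideration. Also in the Synopsis, acuity and refraction testers are masked to the "post-operative target SE up to the completion of the 3 Month Visit". SAP 5.2 summarises target MRSE at baseline.

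**Monovision.** The Introduction says "this modular lens will provide clinical utility in two basic areas, the first being the focus of this study". That first area includes the discussion of monovision, where typically "within three months of the surgery a patient's acceptance or lack of acceptance of monovision correction will be known". The exchange decision is made at the 3 Month Visit. Appendix A Table 1 records the dominant eye preoperatively and again at that visit.

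**The concern.** Uncorrected distance acuity reflects refractive success only in an eye that is meant to see at distance. Two kinds of exchange would break that link.

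- **Near to distance.** The first optic may have hit its near target exactly. The exchange still shows a large UCDVA gain.
- **Distance to near.** The exchange may be fully accurate. It still shows a UCDVA loss.

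In both cases the change score records a change of target, not correction of residual refractive error. The mean change, its confidence interval, the category shifts and the McNemar comparison would mix the two, and the distortion can run in either direction. The results are meant to inform a confirmatory study, so a reader could mistake intended target changes for success or failure of the exchange.

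**Working it through.** The plan gives no effect size, SD, power or sample size for Cohort 2 UCDVA, so there is no figure of its own to reproduce. What follows illustrates sensitivity and is not an estimate.

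**Inputs**

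- N = 44 exchanged eyes, the minimum number of exchanges in Protocol 4.7.1.
- g = mean gain in eyes with a distance target before and after exchange: 0.15 logMAR (assumed; 0.25 as a check).
- L = change in each eye whose target was deliberately moved: 0.3 to 0.5 logMAR (assumed).
- k = number of such eyes. It is not in the documents and is varied from 0 to 8.

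**Mean change.** The mean gain over all eyes is [(N − k) × g − k × L] / N for exchanges to near, and [(N − k) × g + k × L] / N for exchanges from near. For example, with k = 4 to near and L = 0.3: (40 × 0.15 − 4 × 0.3) / 44 = 4.8 / 44 = 0.109.

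| k | To near, L = 0.3 / 0.5 | From near, L = 0.3 / 0.5 |
|---|---|---|
| 0 | 0.150 | 0.150 |
| 2 | 0.130 / 0.120 | 0.157 / 0.166 |
| 4 | 0.109 / 0.091 | 0.164 / 0.182 |
| 8 | 0.068 / 0.032 | 0.177 / 0.214 |

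With g = 0.25, 4 exchanges to near give 0.200 / 0.182, and 8 from near give 0.259 / 0.295. In every row the distance-target eyes alone give g.

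**McNemar comparison at one cut-off.** The protocol does not say which form of the test is meant; the exact two-sided form is assumed here. With b gains and c losses, p = 2 × P(X ≤ min(b, c)), where X is binomial (b + c, 0.5). Counts are assumed, and a changed-target eye counts only if it crosses the cut-off.

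- 8 gains, 0 losses: 2 / 256 = 0.008.
- Add 1 intended loss: 2 × (1 + 9) / 512 = 0.039.
- Add 2 intended losses: 2 × (1 + 10 + 45) / 1024 = 0.109.
- Other direction: 2 gains alone give 2 / 4 = 0.50. Adding 4 near-to-distance gains gives 2 / 64 = 0.031.

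On these assumed counts, two to four changed-target eyes are enough to move the nominal result across 0.05 in either direction.

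**The case against.** **Refractive accuracy is already covered.** Protocol 8.3.2.4 defines EPR as postoperative MRSE minus target. For Cohort 2 it compares absolute EPR with the same eye's 3 Month pre-exchange value, with a 95% confidence interval. Protocol 7.2 and SAP 5.6 add MRSE within 0.50 D and 1.00 D of the exchange target. This stands. A reader might infer that the plan cannot show whether exchange corrects residual error; the documents do not support that.

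**No passage says that a study eye will be given a near target.** The monovision text is background. Variation in targets, masking and the choice of eye all fit distance targets that differ by fractions of a dioptre. This stands as a limit on size. It does not remove the gap, because the visible text neither excludes near targets nor separates them. Some text is blacked out or absent from the public copy, and optic power determination is left to the Surgical Guide, so a target rule could exist elsewhere.

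**A near-to-distance gain can be a real benefit.** Protocol 3.3.4 offers exchange for improved visual function, not only for a refractive miss. This stands, and it is why the all-eyes analysis should remain.

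**The inferential stakes are modest.** A reader might take UCDVA to carry the only significance test that bears on exchanged eyes. Protocol 8.1 and 8.3.2.1 plan a BCDVA test over HMIOL eyes, and 8.1 includes Cohort 2 eyes after exchange. SAP 2 gives the SAP precedence, SAP 5.1 makes p-values nominal, and SAP 4 disclaims definitive conclusions.

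**Simple bounds mislead.** A reader might put the shift in the mean at (k / 44) × 0.5. That holds only if the other eyes do not change. With g = 0.15, k = 8 and L = 0.5, the distance from the distance-target mean is (8 / 44) × 0.65 = 0.118 to near and (8 / 44) × 0.35 = 0.064 from near. Nor is every changed-target eye a discordant pair.

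**Conclusion.** The point holds in limited form. As visible, the plan pools Cohort 2 UCDVA change, acuity categories and (in the protocol only) the McNemar comparison over all exchanged eyes regardless of target. Near targets are allowed and foreseeable, and the pooled results cannot separate a change of target from correction of residual error. EPR and MRSE to target answer the accuracy question but leave the UCDVA tables as they are.

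The size is unknown and could be zero, because the number of near-target or changed-target exchanges is not stated. On the assumed inputs (44 eyes, gain 0.15, changes of 0.3 to 0.5 logMAR), 4 to 8 such eyes would move the mean gain from 0.150 to between 0.109 and 0.032 if all went to near, or to between 0.164 and 0.214 if all came from near. This does not show that the UCDVA results will be wrong, or that the all-eyes analysis should be dropped.

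**What to change.** In Protocol 8.3.2.3 and SAP 5.6:

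1. Keep the all-eyes Cohort 2 UCDVA analysis.
2. Pre-specify the same change with 95% confidence interval, the acuity categories and the McNemar comparison for eyes with a distance target both before and after exchange. Use the recorded targets (target MRSE in SAP 5.2, and the exchange target that the MRSE endpoints already need) and a cut-off fixed before analysis.
3. Report eyes with a near or changed target separately, giving their number and their MRSE against target. Add UCNVA if it is collected at those visits; the Synopsis lists it, but the visible schedule does not confirm it.
4. Base any statement about correction of residual error on the distance-target UCDVA results together with EPR and MRSE to target.

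If only distance targets are intended, a sentence saying so would settle the point.

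**Cost.** One more table and a few sentences, with no new data and no change to care. The subset's confidence interval may be slightly wider. At the same SD, ignoring the small change in the t quantile, the factor is √(44 / 40) = 1.05 if 4 eyes leave and √(44 / 36) = 1.11 if 8 leave.
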